6.7 Visit 9-14; Weeks 7-11

Phone Calls

The subject will receive a phone call from the study coordinator every week (week 7-11). During these phone calls, the study coordinator will review the subjects seizure history, medications changes (started any new or stopped any medication), or had any adverse events (side effects, illness, and/or hospitalizations).

6.8 Visit 12 & 14; Week-9 and Week-11

Option Care Home Infusions

Week-9 infusion (0.6g/kg IVIG) will be given 2 weeks following the 2nd infusion. Week-11 (0.6g/kg IVIG) infusion will be given 2 weeks after the 3rd infusion (total of 5 weeks).

6.9 Visit 15; Week 12

Mayo Clinic Examination

During this visit, patients will be seen in clinic. All required assessments will be documented and signed.

- Review current medication history
- Vital signs (blood pressure, temperature, heart rate, breathing rates, and weight)
- Neurological Examination
- Undergo memory and cognitive function assessments (RBANS/KOKMEN- Neuropsych testing)
- Blood draw to check antibody levels.

- Review Seizure Diary

6.10 Visits 16-31; Weeks 16-56 (IVIG group), Visits 16-60 (Placebo group)

Subjects will be contacted by phone by the study coordinator every four weeks starting at week 16, 20, 24, 28, 32, 36, 40, 44, 48, 52, 56 and week 60 (only Placebo group). During each of these phone calls, the study coordinator will review the subjects seizure history, medications changes (started new or stopped any medications), or had any adverse events (side effects, illness, and/or hospitalizations). The study coordinator will also use the Telephone Interview for Cognitive Status (TICS) questionnaire and the KOKMEN. This is a questionnaire that will ask you to perform certain tasks like subtracting numbers, recalling information and following directions.

6.11 Visits 21 Week 32 (IVIG group), Visit 23 Week 38 (Placebo group)

Mayo Clinic Examination (standard of care) – following 6 months of follow-up.

During this visit, patients will be seen in clinic. All required assessments will be documented and signed.

- Review current medication history
- Vital signs (blood pressure, temperature, heart rate, breathing rates, and weight)
- Neurological Examination
- Blood draw to check antibody levels.
- Review Seizure Diary

6.12 Visits 29 Week 58 (IVIG group), Visit 31 Week 64 (Placebo group)

Mayo Clinic Examination (standard of care) – following the completion of 1 year of follow-up.

During this visit, patients will be seen in clinic. All required assessments will be documented and signed.

- Review current medication history
- Vital signs (blood pressure, temperature, heart rate, breathing rates, and weight)
- Neurological Examination
- Blood draw to check antibody levels.
- Review Seizure Diary

6.13 Early Termination Visit

Mayo Clinic Examination

During this visit, patients will be seen in clinic. All required assessments will be documented and signed. If the patient is unwilling or unable to come to Mayo Clinic, we will attempt to complete as much of the visit over the phone as possible.

- Review current medication history
- Vital signs (blood pressure, temperature, heart rate, breathing rates, and weight)
- Neurological Examination
- Undergo memory and cognitive function assessments (RBANS/KOKMEN- Neuropsych testing)
- Blood draw to check antibody levels.
- Review Seizure Diary

6.14 Primary Aim Study Procedures Schedule

Primary Aim	Visit 1	Visit 2	Visit 3	Visit 4	Visit 5	Visit 6	Visit 7
Procedures	Baseline Visit Randomize 1:1 to IVIG or Placebo (all)	Week-1 Day 1 Mayo Infusion Center	Week-1 Day 2 Mayo Infusion Center	Week 2	Week 3 Mayo Infusion Center	Week 4	Week 5 Mayo Infusion Center
Inclusion/Exclusion Criteria Review	B						
Informed Consent	B						
Medial History	B						
Medication Review	B	B	B	B	B	B	B
Seizure History	B						
Safety Labs (Renal, Hepatic, Chem, IgA)	B						
Antibody Testing (VGKC, LGI1, CASPR2)	B						
Neuropsych Testing (RBANS/KOKMEN/TICS)	B						
Vital Signs (B/P, Temp, Height/Weight)	B	B	B		B		B
Infusion Therapy		B	B		B		B
Study Visit (Clinic)	B						
Seizure Diary/Adverse Events	B	B	B	B	B	B	B
Phone Call				B		B	

B=Both IVIG and Placebo groups

I=IVIG group only

P=Placebo at baseline group

SOC=standard of care

P* only in case of abnormal results at baseline as determined by treating physician.

All visits for the Primary Aim have a +/- 3 day window.

All visits for the Tertiary Aim have a +/- 7 day window.

Primary Aim	Crossover Visit 8	Visit 9	Visit 10	Visit 11	Visit 12	Visit 13	Visit 14	Visit 15
Procedures	Week 6 EOS for IVIG Group Start SOC	Week-7 Day 1 Option care home infusion	Week-7 Day 2 Option care home infusion	Week 8	Week 9 Option care home infusion	Week 10	Week 11 Option care home infusion	Week 12 end of Study Visit Placebo Group-Start SOC
Inclusion/Exclusion Criteria Review								
Informed Consent								
Medial History								
Medication Review	B	P	P	P	P	P	P	P
Seizure History	B							P
Safety Labs (Renal, Hepatic, Chem, IgA)	p*							
Antibody Testing (VGKC, LGI1, CASPR2)	I							P
Neuro psych Testing (RBANS/KOKMEN/TICS)	B							P
Vital Signs (B/P, Temp, Height/Weight)	B	P	P		P		P	P
Infusion Therapy		P	P		P		P	
Study Visit (Clinic)	B							P
Seizure Diary/Adverse Events	B	P	P	P	P	P	P	P
Phone Call		P	P	P	P	P	P	

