3.2 Study Schematic

Patients will be randomized (1:1 ratio) to receive IVIG or placebo (normal saline). The IVIG or placebo dose will be determined based on ideal weight with a dose not to exceed 80 grams. Patients will be given 650 mg acetaminophen (Tylenol®) and Diphenhydramine (Benadryl®) 25 mg PO PRN, may repeat once after 30 minutes if ineffective, 30 minutes prior to IVIG or placebo administration at every infusion. Patients will receive IVIG or placebo (0.5g/kg) daily for 1 day [week 1 day 1], then they will receive IVIG or placebo (1g/kg not exceeding 80g) daily for 1 day [week 1 day 2]. Patients will also receive 500 ml normal saline before and after the higher dose infusion of 1g/kg. Then, once every 2 weeks [week 3 & 5], patients will receive (0.6g/kg) IVIG or placebo for 4 weeks (2 infusions). After completion of all 4 infusions all patients will be again evaluated at Mayo Clinic [week 6].

The primary aim is to demonstrate the efficacy of IVIG relative to placebo in reducing or stopping seizures [$\geq 50\%$ reduction in seizure frequency] in patients with VGKC Ab associated autoimmune epilepsy. At the end of the 5 week trial, all patients in the initial placebo group (n=15) will receive, in an open label fashion with the same premedications and prehydration protocols IVIG. To help speed up the transition for the placebo group, 1 person from the Mayo study staff, not in direct contact with patients or assessment procedures, will be unblinded, to allow for scheduling with Option Care for the future home infusions. Mayo study staff will work with Option Care to get the IVIG infusions scheduled for the placebo group as soon as possible after the patient's 6 week visit to Mayo Clinic. Option Care home infusion agency will administer these patients IVIG (0.5g/kg) 1 day [week 7 day 1] then IVIG (1g/kg not exceeding 80g) for 1 day [week 7 day 2], then once every 2 weeks for 4 weeks (0.6g/kg IVIG) [week 9 and 11]. After completion of all 4 IVIG infusions these 15 patients will be again evaluated at Mayo Clinic [week 12].

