All patients will receive phone calls from the clinical research coordinator at 2 weeks, 4 weeks to assess patient reported side effects and record seizure diary information. The placebo group that will receive IVIG in an open label fashion, will also receive phone calls every week (weeks 7-11) to assess patient reported side effects and record seizure diary information. Any side effects or increase in seizure frequency from previous baseline will be reported to the principal investigator or designee to determine if any action should be taken or if un-blinding is required. Patients will also be given 24 hour emergency contact information for the study team to carry with them at all times.

Treatment location:

First 4 infusions will be given at Mayo Clinic using Mayo's standard operating procedures for infusion administration (see appendix 1). This will allow study personnel to closely evaluate the patient and give the home care network time to set the home treatment.

Home infusions:

The 4 IVIG infusions for those 15 initial placebo group patients will be given at the patient's home or clinic near their home. These infusions will be given per Option Care's standard operating procedure (see appendix 2)

In this study we are going to utilize the home care network of Option Care nationwide. Therefore one of the inclusion criteria is that the home treatment network is available where the patient lives.

Our secondary aim firstly investigates clinical factors predictive of IVIG response. These will include antibody type (LGI1, CASPR2, other) and titer. Thus blood draws will be performed at baseline, 6 weeks and 12 weeks (for placebo only). Secondly, we will assess for improvements in cognitive performance as measured by the KOKMEN¹⁷ and the Repeatable Battery for the Assessment of Neuropsychological Status (RBANS).²⁰

Our tertiary aim, a clinical observational study, investigates factors influencing relapse rate after a positive IVIG response. "Responders" from AIM 1 will be randomly assigned in open label fashion by the treating physician to 2 clinical observational groups:

- Immunotherapy (as per physician/insurance approval): mycophenolate mofetil 2000mg daily or azathioprine 2mg/kg +/- IVIG taper or IVMP taper
- No immunotherapy

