6.4 Visit 5 & Visit 7; Week-3 and Week-5

Mayo Clinic Infusion Center

Week-3 infusion (0.6g/kg drug or placebo) will be given 2 weeks following the 2nd infusion. Week-5 (0.6g/kg drug or placebo) infusion will be given 2 weeks after the 3rd infusion (total of 5 weeks).

6.5 Visit 8; Week 6

Mayo Clinic Examination and Unblinding.

During this visit, patients will be seen in clinic. All required assessments will be documented and signed.

- Review current medication history
- Vital signs (blood pressure, temperature, heart rate, breathing rates, and weight)
- Neurological Examination
- Undergo memory and cognitive function assessments (RBANS/KOKMEN- Neuropsych testing)
- Blood draw to check antibody levels.
- Review Seizure Diary

Then, the study physician and the subject will be unblinded.

If the study subject received placebo, they will be given IVIG in an open label fashion through Option Care Home Infusion service using the same dose and schedule as used for the first portion of this study. The last 4 IVIG infusions for those 15 patients, who received placebo for the first 4 treatments, will be given at the patient's home or clinic near their home. These infusions will be given per Option Care's standard operating procedure. In this study we are going to utilize the home care network of Option Care nationwide. Therefore one of the inclusion criteria is that the home treatment network is available where the patient lives.

If the study subject received IVIG, this will be their Research clinic visit, and they will NOT receive any more infusions for the study, they will only receive the phone calls for long term follow up and proceed to VISIT 16, 26 of the tertiary aim.

6.6 Visit 9 & 10; Week 7: Day 1/Day 2

Option Care Home Infusion

Within a 7-10 days after the subjects Week6 evaluation they will receive the first two infusions through Option Care. The first infusion (0.5mg/kg) IVIG will be followed by the second infusion (1g/kg) being given the very next day.

The IVIG infusion is given over approximately 6-8 hours depending on the dose and rate of the infusion. Prior to the infusion the subject will have an intravenous catheter (IV) placed in the subjects arm which will be removed after each infusion is completed.

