7.2 Endpoints

Primary endpoints*

- 1) Change in seizure frequency

The definition of a “responder” is a patient with a $\geq 50\%$ reduction in seizure frequency.

Secondary endpoints

Clinical factors predictive of immunotherapy response.

The following clinical factors will be analyzed with respect to prediction/correlation with favorable outcome.

- 1) Interval from symptom onset to immunotherapy treatment
- 2) Type of onset
- 2) Clinical course
- 3) Seizure type and frequency
- 4) EEG abnormalities
- 5) Presence of other neurological symptoms or signs (tremor, headache, myoclonus)
- 6) CSF findings (White cell count; protein)
- 7) Neural autoantibody type (LGI1, CASPR2, other) and titer (blood draws will be performed at baseline, 6 weeks and 12 weeks (for placebo group only)
- 8) Change in The Repeatable Battery for the Assessment of Neuropsychological Status (RBANS) scale scores

Tertiary endpoints

For the 1 year follow up “observational study”

- “Responder” patients from Trial will be randomly assigned to 2 clinical groups:
 - Immunotherapy (as per physician/insurance approval): mycophenolate mofetil 2000mg daily or azathioprine 2mg/kg +/- IVIG taper or IVMP taper
 - No immunotherapy
- Subjects will be followed for relapse for a total of 12 months (see study schedule of events).
- Patients will keep a daily seizure diary and record any adverse events while on immunotherapy.
- The study coordinator will call patients every month review seizure history and adverse events.
- Patients will be seen at 6 months and 12 months as part of standard clinical care-neurological examination will be recorded.
- Relapse will be defined as $\geq 20\%$ increase in seizure frequency compared with post IVIG frequency.
- Cognition will be assessed by the study coordinator who will perform Telephone Interview for Cognitive Status and the KOKMEN at each monthly call.
- If relapse occurs, the patient will be seen at the clinic. Patients on no therapy will be started on immunotherapy, those on therapy will have treatment adjusted as per current standard clinical care.

8 Safety and Adverse Events

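### The section 6.14 schedule limits the week-6 antibody test to the IVIG group, but sections 3.2, 6.5 and 7.2 do not

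*Combined protocol and SAP*

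**What the plan says.** **The table.** Section 6.14 codes each procedure by arm: B for both groups, P for the placebo group, and I, defined as "I=IVIG group only". In the second table the antibody row begins "Antibody Testing (VGKC, LGI1, CASPR2) I". That cell falls under Visit 8, headed "Week 6 EOS for IVIG Group Start SOC". The next entry in the row is a P at Visit 15 (week 12). At baseline, in the first table, the row is coded B.

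**The text.** Section 3.2, on the secondary aim, says: "Thus blood draws will be performed at baseline, 6 weeks and 12 weeks (for placebo only"). Section 7.2 repeats this under the predictive factor for autoantibody type and titre: "blood draws will be performed at baseline, 6 weeks and 12 weeks (for placebo group only"). Section 6.5, which describes Visit 8, includes "Blood draw to check antibody levels" in its list of assessments and names no arm. After that list it says: "Then, the study physician and the subject will be unblinded". Section 3.2 also makes the week-6 visit common to both arms: "After completion of all 4 infusions all patients will be again evaluated at Mayo Clinic [week 6"].

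**The concern.** Two parts of one protocol give different instructions for the same blood draw. Study staff often work from the schedule table. If they do so here, no placebo patient has a titre at week 6.

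That would have three consequences for the placebo arm:

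- There is no titre shortly before open-label IVIG begins, so the latest available is the baseline one.
- The change from baseline to week 12 spans both the placebo period and the IVIG period, and the two cannot be separated.
- The gap probably cannot be filled later, because blood for the repository is listed only at screening (section 6.1).

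The table also sits badly with the blind. Under section 5.7 only the research pharmacy and one team member without patient contact know the allocation. Section 6.5 puts the draw before unblinding. In that order, staff could not apply an IVIG-only rule without learning or revealing the arm.

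**Working it through.** The plan gives no figure to reproduce here. The check compares the passages and then counts samples.

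**1. Is the code a fault of table extraction?** The second 6.14 table has eight visit columns, Visits 8 to 15. In the antibody row, I is in column 1 (Visit 8) and P in column 8 (Visit 15). The neuropsychology row has entries in the same two columns, B and then P. Other Visit 8 rows, such as medication review, seizure history and vital signs, read B. Section 6.15 uses the same I and P coding for later antibody tests. The code appears to be what the authors entered.

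**2. Can the text be read to agree with the table?**

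| Source | Week 6, IVIG arm | Week 6, placebo arm |
|---|---|---|
| 6.14 table | yes | no |
| 6.5 | yes | yes |
| 3.2 and 7.2, limit applies to week 12 only | yes | yes |
| 3.2 and 7.2, limit stretched back to week 6 | no | yes |

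No reading of 3.2 or 7.2 gives an IVIG-only draw. The stretched reading gives the reverse of the table.

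**3. Week-6 titres planned** (15 per arm, section 7.1)

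- Text: 15 + 15 = 30.
- Table: 15 + 0 = 15.
- Difference: 30 − 15 = 15, and 15/30 = 50%.

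Section 7.1 allows a maximum dropout of 20%. Assuming this is even across arms and occurs before week 6, each arm has 15 × 0.8 = 12. The text then gives 24, the table 12, and the difference is 12.

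**4. Titres per patient through week 12**

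- Placebo arm: 3 under the text (baseline, weeks 6 and 12) and 2 under the table (baseline and week 12).
- IVIG arm: 2 under either (baseline and week 6).

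**5. Age of the latest titre at the first open-label infusion, placebo arm, nominal schedule**

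- Table: the latest is baseline, taken a few days before week 1 day 1 (section 6.2). From week 1 day 1 to week 7 day 1 is 6 × 7 = 42 days, so the gap is 42 days plus a few.
- Text: the week-6 draw, 7 to 10 days before (section 6.6).

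**6. Is there a pattern behind the table's coding?** Combining 6.14 and 6.15 and subtracting each arm's end-of-IVIG visit:

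- IVIG arm: weeks 6, 32 and 58, minus 6, give 0, 26 and 52.
- Placebo arm: weeks 12, 38 and 64, minus 12, give 0, 26 and 52.

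The coding matches a plan of one titre at 0, 26 and 52 weeks after each arm's IVIG course.

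**The case against.** There are four points on the other side.

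- **The table may be deliberate.** The regular 0, 26 and 52-week pattern suggests so, and section 3.1 mentions collecting samples only when the placebo group returns after open-label IVIG. This stands as evidence about intention, and it is why the remedy must cover both cases. It does not remove the conflict with the three text passages.

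- **The loss of 15 titres is an upper bound.** Blinded staff who work through section 6.5 in order would draw blood from everyone, because they do not know the arm. This stands: the loss occurs only if the table is followed. It also shows that the table cannot be carried out in the order that 6.5 sets.

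- **The harm falls on an analysis that is not specified.** Section 7.2 names titre as a predictor but describes no between-arm comparison of titre change. It does not say whether the placebo arm's open-label response enters the predictor analysis. Baseline titre is coded for both arms. This stands, and it keeps the point minor.

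- **Blood might be available anyway.** The table allows week-6 safety laboratory tests in placebo patients whose baseline results were abnormal, and the documents are otherwise silent on storage. This stands only in part. Nothing provides for keeping such blood, and it would come from selected patients only.

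**Conclusion.** The concern holds as a minor inconsistency. The Visit 8 antibody cell in 6.14 contradicts sections 3.2, 6.5 and 7.2, and it does so whichever way the placebo-only parenthesis is read. If the table is followed, 15 of 30 week-6 titres are lost, all in the placebo arm. With 20% dropout, even across arms and before week 6, it is 12 of 24. If 6.5 is followed, none are lost.

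The effect is limited to one secondary predictor, antibody titre. The primary responder endpoint, its power and the baseline titre are not affected. The documents do not show which version was intended.

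**What to change.** Decide which version is the plan and make the passages agree.

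- **If both arms are to be sampled at week 6:** change the Visit 8 antibody cell in the second 6.14 table from I to B. This is one cell. It adds no assays if the text was already the plan, and at most 15 if the table was.
- **If only the IVIG arm is to be sampled:** correct the wording in 3.2, 6.5 and 7.2, and in 6.5 place the draw after unblinding. This adds no assays, but leaves the placebo arm without a titre just before open-label IVIG.

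The first option is the simpler. It keeps the pre-crossover titre and works within the order of the visit as 6.5 describes it.

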4.2 Exclusion Criteria

- History of thrombotic episodes within the 2 years prior to enrolment
- History of status epilepticus within the last year
- Known allergic or other severe reactions to blood products including intolerance to previous IVIG
- Previous adequate trial of IVIG as determined by the Principal Investigator
- IgA deficiency
- Prior failed trial of high dose steroid (prednisone $>60\text{mg}$ daily or methylprednisolone $>1\text{g}$ weekly for >2 weeks)
- Reproductive status:
 - Women who are pregnant,
 - Women who are breastfeeding,
 - Women and men of childbearing potential who are unwilling or unable to use an acceptable method of birth control to avoid pregnancy for the entire study period, as evaluated by the investigator. (Women of non-childbearing potential are those that have a history of hysterectomy, bilateral oophorectomy, or are postmenopausal with no history of menstrual flow for > 12 months prior to screen visit.)
- Any surgical procedure (except for minor surgeries) within 4 weeks prior to baseline.
- Evidence of serious uncontrolled concomitant diseases that may preclude patient participation (physician determined), as described; Other nervous system disease, cardiovascular disease, hematologic/hematopoiesis disease, respiratory disease, muscular disease, endocrine disease, renal/urologic disease, digestive system disease, congenital or acquired severe immunodeficiency
- Known active infection (excluding fungal infections of nail beds or caries dentium) within 4 weeks prior to baseline.
- Evidence of chronic active hepatitis B or C.
- Active ischemic heart disease in the past year prior to baseline.
- Patients should not have severe renal or hepatic disease (determined by treating physician).
- Severe hypertension (diastolic pressure >120 mmHg or systolic >170 mmHg).

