5.3 Method for Assigning Subjects to Treatment Groups

All patients who are cleared for randomization by their Principal Investigator (PI) or the Sub-Investigator will be randomized on Day 1. The research pharmacy will be performing the 1:1 (drug/placebo) randomization. All patients must remain on randomized treatment assignment until their EOS or Early Termination (ET) Visit.

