6.1 Visit 1 (Screening)

The following will occur at this visit and last up to 4 hours

- Review of medical history
- Review of past and current medication history
- Vital signs (blood pressure, temperature, heart rate, breathing rates, height and weight)
- Neurologic examination
- Undergo memory and cognitive function assessments (RBANS/ KOKMEN Neuropsych testing)
- Review seizure diary
- Confirmation of stable dose of antiepileptic medications

After the assessments are complete and if the subject still meets all study inclusion criteria blood will be drawn for testing. The amount of blood drawn will be approximately 6 tablespoons or 90mL.

This blood test will look at the following:

- kidney and liver function
- Blood sugar and electrolytes

- IgA immunoglobulins
- Antibody testing
- A pregnancy test if you are a female and able to become pregnant
- Blood for repository for future testing

6.2 Visit 2 & 3; Week-1 Day 1 and Day 2

Mayo Clinic Infusions

Within a few days after the subjects initial evaluation they will receive the first two infusions at the Mayo Clinic Infusion Center. The first infusion (0.5g/kg) drug or placebo will be followed by the second infusion (1g/kg) being given the very next day.

The IVIG infusion is given over approximately 6-8 hours depending on the dose and rate of the infusion. Prior to the infusion the subject will have an intravenous catheter (IV) placed in the subjects arm which will be removed after each infusion is completed.

The subject will be given IV fluids (500 mls of normal saline) before and after the infusion of 1g/kg. The subject will be given acetaminophen (Tylenol) (to prevent headache) and Benadryl (to prevent allergic reaction) before all infusions. Before, during and after the infusions, the subject's vital signs will be monitored.

6.3 Visit 4 & 6; Weeks 2 & 4

Phone Calls

The subject will receive a phone call from the study coordinator at week-2 and again at week-4. During these phone calls, the study coordinator will review the subjects seizure history, medications changes (started any new or stopped any medication), or had any adverse events (side effects, illness, and/or hospitalizations).

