8.6.1 Internal Data and Safety Monitoring Plan

1. Subject Safety

All subjects enrolled into this study will undergo safety assessments (vital signs, weight, safety blood tests, and cardiac status) at various time points throughout the study. Any abnormal finding will be reported to the PI immediately upon receiving the results.

Subjects will receive phone calls the week after their infusions in which study seizure diaries will be reviewed at all visits for adverse events and any addition or stoppage of new or current medications. This information will be documented in the subject’s study binder. Any information that is collected and is considered abnormal will also be reported to the PI as soon as possible.

All participants shall have contact information for the study coordinator. Any serious adverse event should be reported to the coordinator within 24-48 hours by the patient. The principle investigator will be informed and take the proper steps to ensure patient safety (reporting to the IRB per institutional guidelines and reporting to the sponsor).

1. Severe allergic reaction that call for hospitalization.
2. Any thrombotic event
3. Status epilepticus
4. Increased seizure frequency (more than 50% compared to base line)

In the event PI is not available, the Co-Investigator will be notified of any abnormal findings.

2. Data Integrity

Study inclusion and exclusion will be reviewed with each potential subject to ensure appropriateness for enrollment into the study. Study documents will be completed at the time of the visit and will be entered into the EDC (electronic data capture) system. All data queries will be adjudicated in a timely manner to ensure transcription of data is accurate and complete. The study monitor will have access to the study files and visits to the laboratory and pharmacy will be pre-arranged for the monitor. The PI/Co-I and study team will be available during the monitoring visits.

3. Subject Privacy

Subjects will be seen on Mayo-8 in a clinical exam room. All subjects will have the study explained to them in detail by a qualified member of the study team. The signing of the consent will not occur until all subjects and/or other family members have had ample time to review the consent form and have all their questions answered by the study team.

4. Data Confidentiality

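### Placebo patients start open-label IVIG about 6–7 weeks after Visit 1 with no further pregnancy test scheduled, and with a repeat renal/hepatic panel only if the baseline was abnormal

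*Combined protocol and SAP*

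**What the plan says.** Section 6.1 includes in the Visit 1 blood work "A pregnancy test if you are a female and able to become pregnant". No later visit list repeats it, and the schedule tables in 6.14 and 6.15 have no row for it.

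In 6.14 the safety laboratory row (renal, hepatic, chemistry, IgA) is marked for both arms at Visit 1. Its only later entry is `p*` at Visit 8 (week 6), explained as "P* only in case of abnormal results at baseline as determined by treating physician". The only blood draw in the 6.5 text for Visit 8 is for antibody levels. Review of inclusion and exclusion criteria is marked at Visit 1 only.

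At Visit 8, after the assessments, "Then, the study physician and the subject will be unblinded". Section 6.5 continues: "If the study subject received placebo, they will be given IVIG in an open label fashion through Option Care Home Infusion service". It attaches no safety condition. Section 6.6 sets the timing: "Within a 7-10 days after the subjects Week6 evaluation they will receive the first two infusions through Option Care".

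Two other provisions bear on this. Section 5.3 has an investigator clearance, but it is for randomization: "All patients who are cleared for randomization by their Principal Investigator (PI) or the Sub-Investigator will be randomized on Day 1". Section 8.6.1 says that all subjects "will undergo safety assessments (vital signs, weight, safety blood tests, and cardiac status) at various time points throughout the study", without naming visits.

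**The concern.** Section 4.2 excludes pregnant women and patients whom the physician judges to have severe renal or hepatic disease. Testing at Visit 1 means that the IVIG arm is checked a few days before its first dose. For the placebo arm the same tests precede saline, and first exposure to the drug comes weeks later.

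The setting adds to this. Section 3.2 places the first four infusions at the study clinic so that staff can observe patients closely, but placebo patients receive saline there. Their first IVIG is given at home or nearby, so Visit 8 is the last study-clinic visit before it.

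At stake is a placebo patient who becomes pregnant after Visit 1, or whose renal or hepatic function worsens without symptoms. That patient could receive the two largest-exposure days of the regimen before anyone knows. The `p*` rule follows up a problem already seen at baseline and cannot find a new one.

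**Working it through.** **Where the tests fall (6.1 to 6.9 and 6.14)**

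| Contact | Pregnancy test | Renal/hepatic panel |
|---|---|---|
| Visit 1 | listed | all patients |
| Visits 2–7 | none | none |
| Visit 8 (week 6) | none | placebo arm, only if baseline abnormal |
| Visits 9–15 | none | none |

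Over Visits 2–15 (14 visits) there are 0 scheduled pregnancy tests and 0 unconditional renal/hepatic panels.

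**Time to first open-label IVIG**

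- Plan's own figure (3.2, 5.2): week 7 day 1, which is 6 × 7 = 42 days after week 1 day 1.
- Rebuilt from the infusion spacing (6.2, 6.4): infusions on day 1, day 2, day 2 + 14 = 16, and day 16 + 14 = 30. The week 6 visit is assumed to fall on day 36–37, about a week after infusion 4. Adding the 7–10 days of 6.6 gives day 43–47, or 42–46 days after Day 1. The lower end matches the plan's 42 days.
- Visit 1 to Day 1: 6.2 gives only a few days. Assumed 2–5 days.
- Visit 1 to first open-label IVIG: 42 + 2 = 44 to 46 + 5 = 51 days, or 6.3–7.3 weeks. With the ±3-day window of 6.14: 41–54 days, or 5.9–7.7 weeks.
- Sensitivity: with the nominal 42 days and a gap of 1–7 days, 43–49 days (6.1–7.0 weeks). If the week 6 visit falls on the last day of that week, with a 10-day wait and a 5-day gap, 41 + 10 + 5 = 56 days (8.0 weeks).

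**Time from last scheduled tests to IVIG, by arm**

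The fourth infusion follows the first by 1 + 14 + 14 = 29 days.

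| | First IVIG | Fourth IVIG |
|---|---|---|
| IVIG arm, from Visit 1 | 2–5 days | 31–34 days |
| Placebo arm with normal baseline, from Visit 1 (as written) | 44–51 days | 73–80 days |
| Placebo arm, from Visit 8 (if tested there) | 7–10 days | 36–39 days |

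**Dose resting on the Visit 1 results** (doses from 3.2 and 5.2; 6.6 prints the first one in mg/kg)

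0.5 + 1.0 = 1.5 g/kg over two days; 1.5 + 0.6 + 0.6 = 2.7 g/kg over the course. Both are before the 80 g cap.

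**How many patients**

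At most 15 of 30, the size of the placebo arm. The number of women of childbearing potential is not given, and the documents supply no rate for pregnancy or for silent renal or hepatic change. No event probability can be computed.

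**The case against.** The laboratory half is a stated choice. The footnote is an explicit rule under the physician's judgement. Between Visit 1 and Visit 8 these patients receive only saline and may neither change antiepileptic drugs nor start immunosuppressants (5.5). That stands, and it is why the pregnancy test, for which no rationale is given, is the stronger part.

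No document sets a validity period for screening results, so 6–7 weeks breaches nothing. The IVIG arm also receives all its doses on Visit 1 results, and the fix itself would leave 36–39 days before the fourth dose. This also stands. The point does not rest on a cut-off. It rests on testing close to first exposure, which the plan does for one arm and not for the other.

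The existing protection is real: required contraception (4.1), an in-person Visit 8 with vital signs and neurological examination, adverse-event questions at every contact (8.2), weekly calls in weeks 7–11, vital signs around each home infusion (6.6), ideal-weight dosing with a cap, and the power to stop treatment for safety (4.4.1). None of these reliably detects an unrecognised pregnancy or a symptom-free laboratory change. The undated tests in 8.6.1 add no scheduled test before crossover.

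The home agency's procedure (appendix 2) is not in the text and may contain pre-infusion checks. This cannot be resolved from the documents.

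A reader might infer that all of 4.2 should be rechecked before crossover, with a hold for recent surgery, infection, thrombosis, status epilepticus or hypertension. The documents do not support going that far. Thrombosis and status epilepticus are already withdrawal and stopping criteria (4.4.1, 8.5), and the others would probably surface at Visit 8 or on the calls. A long hold list could also delay treatment that 3.2 wants started promptly.

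**Conclusion.** The gap is real but modest. As written, a placebo patient with a normal baseline gets first IVIG about 6–7 weeks after the only scheduled pregnancy test and renal/hepatic panel. A new pregnancy or a new silent renal or hepatic change could be missed before 1.5 g/kg is given over two days. The interval assumes 2–5 days from Visit 1 to Day 1 and a week 6 visit on day 36–37. Other reasonable readings give about 6 to 8 weeks.

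Three stronger readings should be avoided. Fifteen is the size of the arm, not the number at risk: those at risk are some subset of it, and the absolute risk is unknown and probably low. A silent change need not amount to the severe disease that 4.2 excludes; that remains the physician's judgement, which a current panel would inform. Efficacy is not affected, because the randomized comparison ends at week 6.

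This is a cheap safety improvement of low-to-moderate priority. Confidence is medium, because appendix 2 is unseen.

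**What to change.** In 6.14 at Visit 8, add a pregnancy test for placebo-arm women of childbearing potential, and change `p*` to `P` for the renal/hepatic panel.

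In 6.5, after the sentence that gives open-label IVIG to placebo patients, add: *The investigator reviews the Visit 8 pregnancy test and renal/hepatic results before the first home infusion; IVIG is not started if the patient is pregnant, or while the investigator judges that severe renal or hepatic disease (4.2) is present.*

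No wider eligibility recheck is needed. Drawing the blood after the Visit 8 unblinding avoids sampling the IVIG arm. If appendix 2 already requires equivalent checks, citing them in 6.5 would settle the point.

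Cost: up to 15 panels and a few pregnancy tests at an existing visit, possibly one extra draw per placebo patient, and review time that should fit within the existing 7–10 days. The change shortens the untested interval before first exposure to those 7–10 days; it does not remove it.
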